9.3. Variables

9.3.1. Exposure

Among the eligible cohort of live birth pregnancies linked to an infant (Primary Objective and Secondary Objective 1 cohort) and among the cohort of all eligible live birth and non-live birth pregnancies (Secondary Objective 2 cohort), HZ/su exposure will be defined as receipt of at least one dose of HZ/su during pregnancy. HZ/su vaccination will be identified by means of CPT code 90750 and National Drug Code (NDC) codes 58160-828-01, 58160-829-01, 58160-819-12, 58160-828-03, 58160-829-03, and 58160-823-11. We may include additional codes for identification of HZ/su exposure if relevant codes become available in the future. Pregnancies among women receiving at least one dose of HZ/su during pregnancy will be considered exposed. If a woman receives the vaccine before the start of pregnancy but does not receive the vaccine during the 30-day pre-pregnancy period or during pregnancy, she will not be considered exposed and would be considered for the comparator unexposed group. As described in Section 9.2.1.2, exposure will be further categorized by stages of pregnancy: pre-pregnancy, first trimester, second trimester, third trimester.

214420 (EPI-ZOSTER-039 VS US DB) Protocol Amendment 2 Final

9.3.2. Outcomes (Amended 15 August 2022)

Outcomes to be evaluated include MCMs and additional infant/birth outcomes (preterm birth, SGA, LBW, NICU admission and neonatal death), complications of pregnancy (placental abruption, preeclampsia and eclampsia) and pregnancy outcomes (live birth, non-live birth [stillbirth and spontaneous abortion]). The primary outcome of this cohort study is MCMs of the infants.

As indicated in Section 9.2.1., the IC diagnoses of pregnant women and pregnancy outcomes will be identified from the health plan claims of the DRN containing ICD-10-CM Codes for IC conditions *and validated coding algorithms for IC conditions* during the period 273 days prior to the pregnancy start date through the first trimester (98 days after the pregnancy start date).

MCMs will be confirmed through chart review. Other outcomes will not be confirmed through chart review. Many of these ICD-10-CM algorithms for the secondary outcomes have not yet been validated. We will conduct a literature search prior to final analysis to determine potential validated algorithms for these secondary outcomes. Recent published studies provide evidence of the validity of ICD-10-based algorithms to identify adverse pregnancy outcomes. An international study reported moderate to high PPVs for ICD-10 codes for select secondary outcomes proposed in this study: 76.4% for LBW; 70.4% for SGA; 81.2% for preeclampsia [Watson, 2021].

Another recently published study in a US population reported higher PPVs for ICD-10-CM codes for preeclampsia and eclampsia (ranging from 89-100%) [Labgold, 2021]. In addition, an ongoing Sentinel COVID-19 pregnancy study, used ICD-10-CM codes to identify adverse pregnancy outcomes including preeclampsia/eclampsia, SGA and LBW. These algorithms were approved by the FDA team in the Hua 2021 study. Pregnancy episodes ending in a non-live birth pregnancy outcome will be identified using validated algorithms developed through Sentinel and non-Sentinel (e.g., VSD) projects [Andrade, 2021; Naleway, 2021].

9.3.2.1. Infant/Birth Outcomes (Primary Objective and Secondary Objective 1)

Infant/birth outcomes to be evaluated include MCMs, preterm birth, SGA, LBW, NICU admission, and neonatal death. These outcomes will be identified in claims data through diagnosis codes among live births for which the mother and infant are linked (Section 9.2.1). Codes for placental abruption, preeclampsia, and eclampsia will be identified in the mothers' claims. For selected outcomes (MCMs, SGA, LBW, NICU), both the infants' and mothers' claims will be searched to ensure more complete capture of infants' diagnoses. The infant's diagnoses may be captured in the mother's health plan claims data shortly after birth (generally \leq 30 days after birth) especially when there is a delay in the enrolment of the infant in the health plan.

9.3.2.1.1. Major Congenital Malformations

An MCM (birth defect or structural defect) is defined as a defect, which has either cosmetic or functional significance to the child (e.g., cleft lip). A detailed list of all major congenital malformations observed in live births compiled from the National Birth Defects Prevention Study (NBDPS) and the European Surveillance of Congenital Anomalies is provided in Appendix G Major Congenital Anomalies [Boyd, 2011; CDC, 2020; Rasmussen, 2003]. Consistent with the NBDPS case definition criteria, potential cases that occur as part of a genetic syndrome or other syndrome of known etiology (Appendix D: Diagnosis Codes for Chromosomal or Genetic Anomalies), or those that occur secondary to other major malformations (e.g., holoprosencephaly or amniotic band sequence) will not be included in the calculation of prevalence of major congenital malformations. Data for infants will be collected from delivery to 1 year of age, health plan disenrollment, death, or end of dataset (whichever comes first). Relevant codes will also be identified in the mothers' claims data for the first 30 days after the infant's date of birth.

MCMs identified from this study will be reviewed by board certified teratologists to confirm the diagnosis. The teratologists will review the medical charts of each potential case and be blinded to treatment. Only validated cases will be used in the main analyses.

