9. RESEARCH METHODS

9.1. Study design

A population-based, non-interventional cohort study will be performed to identify and assess birth and pregnancy outcomes from HZ/su exposed pregnancies among women ages 18-49 years with IC conditions. A comparison group of pregnancies among women with IC conditions who were not exposed to HZ/su during pregnancy will be included and will serve as a reference to account for the contribution of different IC conditions on the safety outcomes of interest. The study will be conducted using health data held by three Data Partners that participate in the FDA's Sentinel System (described in Section 9.4).

The study period for identification of exposed and unexposed pregnancies for the cohort study will be July 1, 2021 to June 30, 2026. MCMs and additional infant outcomes (preterm birth, SGA, LBW, NICU admission, neonatal death) will be assessed in pregnancies resulting in a live birth for which the mother is linked to an infant. Since infant outcomes are generally captured in the infant's health plan claims, the mother's and infant's claims will be linked (see Section 9.2.1). Infants born from these pregnancies (exposed and unexposed) will be followed for up to one year of age for assessment of MCMs, the primary outcome of interest. Pregnancy outcomes will be assessed in pregnancies resulting in a live birth, non-live birth (stillbirth, spontaneous abortion).

214420 (EPI-ZOSTER-039 VS US DB) Protocol Amendment 2 Final

MCMs identified from this study will be validated by board certified teratologists. The teratologists will review the medical charts of each potential case and be blinded to treatment. Only validated cases will be used for main descriptive or comparative analyses (see Section 9.3.2).

Prior to initiating a cohort study, a feasibility assessment will be conducted (see Section 9.6.1.1) to identify counts of exposed live birth pregnancies during the period July 1, 2021 to June 30, 2023. If the feasibility assessment determines that it is not possible to identify an adequate number of exposed live birth pregnancies (see Section 9.5) among women with IC conditions for a cohort study (i.e., $\geq 1/3$ overall target), a descriptive analysis will be conducted (Section 9.7.3). The descriptive analysis will include HZ/su exposed and unexposed pregnancies (live birth and non-live birth pregnancies) among women with IC conditions identified in the feasibility assessment and their infants.

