The DPs use the Sentinel Common Data Model (SCDM) for standardization of demographic and clinical data elements [Curtis, 2012; Sentinel]. Publicly available routine analytical tools include reusable, modular Statistical Analysis System (SAS) programs. These analytical tools are designed to be executed against the SCDM to permit rapid queries, including descriptive analyses and complex methodologies (e.g., comparative analyses), across DPs. Specific information in the SCDM includes, but is not limited to, the following types of data:

- Enrollment data: One record per covered individual per unique enrollment span is included in the SCDM. Individuals are assigned a unique identifier by their insurer, which is linkable to all other data in the SCDM. Due to changes in employment status, individuals may be enrolled multiple times with the same insurer, and the length of each given enrollment "span" may vary substantially. Each record in the enrollment file indicates the patient identifier, enrollment start and end dates, and whether the patient was enrolled in medical coverage, pharmacy coverage, or both during that range. Likewise, a final field indicates whether the DP can request medical charts for a given patient during a given enrollment span.
- **Demographic data**, including birth date, sex, race/ethnicity, and ZIP code of their most recently recorded primary residence.
- Pharmacy dispensing data, including the date and NDC identifier for each dispensed prescription, the nominal days' supply, and the number of individual units (pills, tables, vials, etc.) dispensed. Products purchased over-the-counter or at some cash-only retail locations selling prescription drug products (e.g., through the Walmart Prescription Program) are not captured.

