In addition to access to health plan claims data, all DPs have experience in medical chart retrieval procedures. The expected timeline for chart retrieval is generally between 3 to 6 months, depending on the facility/provider's willingness to participate. Many factors affect retrieval, including the number of facilities/providers to which outreach must be conducted, the type of chart (inpatient vs. ambulatory and whether an electronic health record (EHR) is accessible), and how far back records are requested. We expect chart reviews to be conducted for approximately 5% of pregnancies based on validation studies [Andrade, 2013; Cheetham, 2020; Cooper, 2008; Hansen, 2016; He, 2020]. It is anticipated that approximately 70-85% of requested charts will be returned with enough information (i.e., complete chart) to determine the presence or absence of MCM. Typically, the completeness of medical chart retrieval depends on the type of chart, the facility/provider, how many charts requested, and the type of information.

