9.5. Study size

All pregnancies among women who meet the study inclusion/exclusion criteria will be included in this study.

As the IC conditions included are heterogeneous and the number of MCMs for the primary outcome is likely small, the prevalence of each MCMs among each IC condition under study is not available. For sample size calculation for the cohort study, we employed the prevalence of overall MCMs (3%) in the general population [Holmes, 1976; Leppig, 1987; Marden, 1964; Van Regemorter, 1984] which might have a lower prevalence than among women with IC conditions. Therefore, the sample size calculated is relatively conservative. Assuming a 1:3 ratio of HZ/su-exposed to unexposed, a type 1 error of 0.05, and a target risk ratio of 2.0 for the primary safety outcome of MCMs, 711 live birth infants (live birth pregnancies linked to infant records) from the HZ/su-exposed group and 2133 live birth infants from the unexposed group will allow us to achieve 90% power.

The Power Analysis and Sample Size software (NCCS Statistical Software) was used in the sample size calculation.

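### The main analysis counts only chart-validated malformations, but the protocol neither says how flagged infants without an adequate chart are classified nor allows for them in the 90% power claim

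*Protocol*

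**What the plan says.** Major congenital malformations (MCMs) are found from claims codes and then confirmed by teratologists from the medical chart. Protocol Section 9.3.2.1.1 fixes the consequence: "Only validated cases will be used in the main analyses". Section 9.1 extends it to both branches of the study: "Only validated cases will be used for main descriptive or comparative analyses".

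On the charts, Section 9.4 says "We expect chart reviews to be conducted for approximately 5% of pregnancies based on validation studies" and expects "approximately 70-85% of requested charts will be returned with enough information (i.e., complete chart) to determine the presence or absence of MCM".

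The exclusion criteria in Section 9.2.1 do not mention a missing or incomplete chart, and Section 9.5 includes every eligible pregnancy. For the sample size, "we employed the prevalence of overall MCMs (3%) in the general population". With a 1:3 ratio, type 1 error 0.05 and a target risk ratio of 2.0, Section 9.5 gives 711 exposed and 2133 unexposed infants for 90% power. Retrieval does not enter that calculation.

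Section 9.7.2.3 promises sensitivity analyses for outcome misclassification, with detail in the SAP. Section 9.7.3 rules out analyses beyond prevalence and confidence intervals if the study falls back to the descriptive branch. In the ENCePP checklist (Annex 10), handling of missing data is marked No and analytic control of outcome misclassification N/A. The limitations in Section 9.9.1 do not mention chart non-retrieval.

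**The concern.** A flagged infant whose chart is absent or inadequate has an unknown outcome. Under a validated-cases-only rule with no exclusion, that infant is counted with those whose chart refuted the code. The protocol's own planning figure puts 15-30% of requested charts in this state.

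Two things are at stake. The absolute MCM prevalence would be too low in both groups; this matters most in the descriptive fallback, where prevalence is the only output. Fewer confirmed events also mean that the stated 90% power is not reached at the stated size.

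**Working it through.** **Inputs.** Retrieval r = 0.70 to 0.85 and 5% of pregnancies reviewed (Section 9.4). Prevalence 3%, ratio 1:3, type 1 error 0.05, effect 2.0, 711/2133 (Section 9.5).

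**Assumptions.** Two-sided test; all true MCMs are flagged; retrieval is unrelated to true status and equal in the two groups; the chart-level figure applies to infants.

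**Step 1: reproduce the plan's figure.** The two-proportion formula with pooled variance under the null is

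power = Φ[(|p1 − p2| − 1.96·se0)/se1], where se0 = √[p̄(1 − p̄)(1/711 + 1/2133)] and se1 = √[p1(1 − p1)/711 + p2(1 − p2)/2133].

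- Effect read as an odds ratio of 2: p1 = 0.06/1.03 = 0.0583 against p2 = 0.03. The required exposed number is 711 exactly, with power 90.0%. The same reading gives 812 at 1:2 and 1109 at 1:1; Section 9.2.1.3 states 812 and 1108.
- Effect read as a risk ratio of 2: p1 = 0.06. The required exposed number is 641, and power at 711/2133 is 92.5%.

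Both readings are carried forward.

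**Step 2: loss of cases.** Share lost = 1 − r = 15% to 30%. Confirmed prevalence is 3% × 0.85 = 2.55% or 3% × 0.70 = 2.1%. If 5% of 2844 infants is taken as the number of requests, there are about 142 requests, of which 142 × 0.15 ≈ 21 to 142 × 0.30 ≈ 43 stay unresolved.

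Removing these infants from the denominator barely helps: 2.55%/(1 − 0.05 × 0.15) = 2.57% and 2.1%/(1 − 0.05 × 0.30) = 2.13%. The loss is in the numerator either way.

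**Step 3: events and power.** Both prevalences are multiplied by r. Expected events below use the risk-ratio reading (for example 711 × 0.06 × 0.85 = 36.3).

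| r | Expected confirmed events, exposed + unexposed | Power, odds-ratio reading | Power, risk-ratio reading |
|---|---|---|---|
| 1.00 | 42.7 + 64.0 = 106.7 | 90.0% | 92.5% |
| 0.85 | 36.3 + 54.4 = 90.7 | 85.1% | 88.2% |
| 0.70 | 29.9 + 44.8 = 74.7 | 78.3% | 81.9% |

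Worked example, odds-ratio reading, r = 0.85: p1 = 0.0495, p2 = 0.0255, p̄ = 0.0315, se0 = 0.00756, se1 = 0.00882. Then (0.0240 − 1.96 × 0.00756)/0.00882 = 1.04, and Φ(1.04) ≈ 0.85.

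The exposed number needed for 90% power becomes 842 (r = 0.85) or 1030 (r = 0.70) on the odds-ratio reading, and 760 or 929 on the risk-ratio reading. Fisher's exact test, risk-ratio reading, gives 92.1%, 87.3% and 80.2% for r = 1, 0.85 and 0.70.

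**Step 4: the comparison.** Observed risk ratio = true risk ratio × (exposed retrieval/unexposed retrieval). With equal retrieval the factor is 1 and a true ratio of 2.0 stays 2.0. As an illustration only, putting the two groups at opposite ends of the stated range gives factors of 0.70/0.85 = 0.82 and 0.85/0.70 = 1.21.

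**The case against.** The strongest reply is that the protocol nowhere says an infant without a chart is a non-case, and that such classification is SAP detail. The first part is right: the non-case status is the default that follows from validated-only counting with no exclusion. Step 2 shows, however, that dropping such infants loses the same cases. The second part is only partly right. The validated-only rule and the 90% figure are in the protocol itself. Section 9.7.2.3 offers sensitivity analyses, which leave the main analysis as it is, and Section 9.7.3 closes off even those in the fallback. Section 9.7.4 also says that major changes to the primary endpoint definition or its analysis would come by protocol amendment.

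Confirmed-only is a defensible high-specificity definition, and it can stay as the headline result. Section 9.5 also says 3% may be below the prevalence in immunocompromised women. That could absorb the loss, but only if true prevalence were about 3%/0.85 = 3.5% to 3%/0.70 = 4.3%, which the protocol does not show.

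Three stronger readings are tempting but not supported:

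- **That the exposed-unexposed comparison is biased as written.** No section says retrieval differs by exposure, reviewers are blinded, and matching is within Data Partner. Section 9.4 ties retrieval to provider willingness and chart type, neither of which is a matching variable or a listed propensity score variable, so a check is warranted. A bias is not established.
- **That 5% reviewed times 70-85% usable leaves too few charts for the planned events.** The 5% may mean reviews completed rather than requested, and it may be a background rate that would rise if exposure doubled the risk.
- **That further infants are lost because charts cannot be requested for some enrollment spans.** Section 9.4 notes that "a final field indicates whether the DP can request medical charts for a given patient during a given enrollment span", but this describes the data model. No figure shows that any relevant span is affected.

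**Conclusion.** The concern holds for absolute prevalence and for power. If retrieval is unrelated to true status and the 70-85% applies at infant level, following the plan understates confirmed MCM prevalence by 15-30% in relative terms. It also puts power about 5 to 12 percentage points below the stated 90% on the odds-ratio reading. On the risk-ratio reading, power is about 2 to 8 points below 90%. The 15-30% includes charts returned incomplete, not only those never obtained. If true cases have better or worse charts than average, the loss would be smaller or larger. The risk ratio is essentially unbiased under equal retrieval. Whether retrieval is equal is unknown, and the protocol plans no check.

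**What to change.** - In Sections 9.1 and 9.3.2.1.1, classify each flagged infant as confirmed, refuted or not adjudicated, and state that the third group is not treated as confirmed negative.
- Report chart retrieval by exposure group.
- Beside the confirmed-only result, give an all-flagged bound and a simple weighted estimate: confirmed + not adjudicated × confirmed/(confirmed + refuted). State in advance whether that proportion is pooled or taken by exposure group.
- Amend Section 9.7.3 so that the same results are given in the descriptive fallback.
- In Section 9.5, restate expected confirmed events and power with 70-85% retrieval, and say whether 2.0 is a risk ratio or an odds ratio.

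The weighting should stay simple. At 5% flagged, about 36 of 711 exposed infants would have charts requested and about 25-30 would be usable, too few for imputation or weighting by many strata. Restricting the cohort to spans where charts can be requested is not advised, since it could discard scarce exposed pregnancies for an unquantified gain.

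The cost is protocol and SAP wording, a little more analysis on data already collected, and a less favourable power statement. Keeping 711 and stating the lower power leaves the feasibility threshold of 237 unchanged; raising the target would move it. The rule should be fixed before outcomes are seen.

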9.3.2.1.2. Small for Gestational Age

SGA (ICD-10-CM P05.0X, P05.1X) infants will be identified by searching both the infant's and mother's claims for the first 30 days after the infant's date of birth. While a prior study has reported a low sensitivity for the ICD-9-CM code for SGA, the positive predictive value (PPV) and specificity were high [Phiri, 2015]. Although the sensitivity of the SGA code was low, this study also showed that if misclassification is non-differential with respect to exposure, the relative risk estimates will be nearly unbiased for evaluations of factors associated with SGA.

9.3.2.1.3. Preterm Birth

A preterm birth occurs if the gestational age at birth is < 37 completed weeks. Pregnancy periods of < 37 weeks duration will be identified. International Classification of Diseases, Tenth Revision, Clinical Modification (ICD-10-CM) codes for preterm delivery and for gestational age < 37 weeks (Appendix F). Codes to Identify Preterm and Post-term Birth) are incorporated in the algorithm to determine pregnancy periods.

9.3.2.1.4. Low Birth Weight

LBW is a birth weight of < 2,500 grams. LBW (ICD-10-CM P05.0X, P07.0X, P07.1X) infants will be identified by searching both the infant's and mother's claims for the first 30 days after the infant's date of birth.

214420 (EPI-ZOSTER-039 VS US DB) Protocol Amendment 2 Final

9.3.2.1.5. NICU Admissions

NICU admissions (CPT codes 99468, 99469) will be identified by searching both the infant's and mother's claims for the first 30 days after the infant's date of birth. A prior study reported a high PPV for NICU codes recorded in the mother's and infant's claims data (PPV=92%) [Andrade, 2012].

9.3.2.1.6. Neonatal Deaths

Potential infant deaths during the 28 days after birth will be identified in hospital discharge disposition data included in the health plan claims files.

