- Participant meets study definition of SLE, MS, RA, IBD, PsO/PsA, SOT, SCT, HM, ST, or HIV (see Appendix A: ICD-10-CM Codes for IC and Appendix B: Validated Coding Algorithms for IC conditions). Codes for IC conditions will be identified in the health plan claims of the DRN during the period 273 days prior to the pregnancy start date through the first trimester (98 days after the pregnancy start date). Diagnoses recorded through the first trimester will be included to account for women who may not have frequent visits prior to pregnancy and may have a more complete assessment of medical conditions during the first prenatal care visit.
- Participant has at least 273 days of continuous health plan enrollment with medical and drug benefits prior to the start of pregnancy through the delivery date, with gaps of up to 45 days in coverage being permitted. The 273-day pre-pregnancy period through the first trimester (a period of 98 days after the pregnancy start date) was chosen to allow identification of potential confounders of interest (Section 9.3.3). In Sentinel projects, gaps of 45 days or less in health plan enrolment are

214420 (EPI-ZOSTER-039 VS US DB) Protocol Amendment 2 Final

typically considered administrative gaps (and not lapses in health plan coverage) and ignored.

Pregnancies will be excluded from the study if the following exclusion criterion is met:

- Participant was exposed to a medication(s) that presents a known increased risk for fetal malformations (see Appendix C: Teratogenic and Fetotoxic Medications)
- Participant delivered an infant identified as having a chromosomal or genetic anomaly (Appendix D: Diagnosis Codes for Chromosomal or Genetic Anomalies
- Ectopic pregnancies, molar pregnancies or induced abortions.
- Multigestation (e.g., twin) pregnancies.

For analyses evaluating infant outcomes (Primary Objective and Secondary Objective 1), the cohort will include pregnancies resulting in live births for which the mother is linked to an infant. Each Sentinel Data Partner will be responsible for linking mothers to infants using all available local data resources. Algorithms linking mothers to infants will vary across Data Partners, generally looking for equivalent health plan subscriber numbers, delivery dates and dates of birth, and shared names and addresses. Sentinel Data Partners are able to link approximately 74% of their infants to their mothers [Sentinel Initiative, 2018].

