9.9. Limitations of the research methods

9.9.1. Limitations of the research methods

Several limitations are inherent in the conduct of studies of vaccine exposures during pregnancy with healthcare databases. The algorithms used to define data study variables may be imperfect and these rely on the accuracy and precision of coding for these items. As a result, misclassification of exposures, outcomes, and potential confounders can occur. In addition, only medically attended events are recorded in the healthcare database, thereby missing events without medical attendance such as early spontaneous abortions. Early fetal losses are often not captured in claims databases (or other data sources) but are generally reported to be mainly associated with chromosomal abnormalities [Zhang, 2018], which would likely not be related to vaccine exposures. In addition, some secondary outcomes of interest will be rare and may be difficult to assess within the study period (e.g., neonatal death). Neonatal deaths will only be captured in hospital discharge data which may lead to under ascertainment of this outcome.

Although appropriate methodologies (e.g., propensity score matching) will be applied to statistically adjust for differences between exposed pregnancies versus unexposed

214420 (EPI-ZOSTER-039 VS US DB) Protocol Amendment 2 Final

pregnancies in this study, it is possible that residual confounding may be present. In addition, depending on the number of events observed, we may be limited in the ability to include additional covariate information in regression models. Some potential covariates are incompletely captured in the health plan data, e.g., over-the-counter (OTC) folate intake, alcohol use, and tobacco use. This limitation relates to the constraint about claims databases. Some confounders (e.g., alcohol use) will not be completely captured although we do not expect the capture will differ by the exposure. We will conduct a sensitivity analysis to exclude such variables and treat them as unmeasured confounders. A detailed description of the bounding factor is provided in the SAP Section 8.7.1 to estimate the magnitude of effect of an unobserved confounder needed to change the statistical inference. We will also compare the results with and without such covariates.

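### Neonatal death is not among the infant outcomes searched in the mother's claims, and the protocol does not say whose files are used, so deaths before the infant has its own record may be missed

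*Protocol*

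**What the plan says.** Section 9.3.2.1 of the protocol lists six infant outcomes: major congenital malformations, preterm birth, small for gestational age, low birth weight, NICU admission and neonatal death. For four of them it plans a search of two files: "For selected outcomes (MCMs, SGA, LBW, NICU), both the infants' and mothers' claims will be searched to ensure more complete capture of infants' diagnoses". The reason follows: "The infant's diagnoses may be captured in the mother's health plan claims data shortly after birth", generally within 30 days, "especially when there is a delay in the enrolment of the infant in the health plan".

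The outcome subsections carry this through. NICU admission, for example, "will be identified by searching both the infant's and mother's claims for the first 30 days after the infant's date of birth".

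For neonatal death, section 9.3.2.1.6 says: "Potential infant deaths during the 28 days after birth will be identified in hospital discharge disposition data included in the health plan claims files". No diagnosis code is given, and neither the infant's nor the mother's file is named.

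On the population for infant outcomes, section 9.2.1 says "the cohort will include pregnancies resulting in live births for which the mother is linked to an infant". Section 9.9.1 adds that linkage is about 70% to 80% and that unlinked infants are left out. On neonatal death, it says: "Neonatal deaths will only be captured in hospital discharge data which may lead to under ascertainment of this outcome".

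**The concern.** The protocol recognises that an infant's early data can be filed under the mother, and it extends the search for that reason. The outcome whose whole window lies in that early period is left out of the extension. A newborn who dies before enrolment is also the kind of infant least likely to have a record to link to, and the analysis counts only linked infants. Entry to the cohort could then depend in part on the outcome being measured.

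Secondary Objective 1 asks for the prevalence of neonatal death. If feasibility fails, section 9.7.3 reports prevalence and confidence intervals and nothing more. Missing the earliest deaths would make that prevalence too low, and a reader of section 9.9.1 would not learn why.

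**Working it through.** The protocol gives no neonatal death rate, timing or capture figure, so there is no stated result to reproduce. The check is a comparison of sections, followed by an identity showing what would be needed to size the loss.

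**1. Windows.** Neonatal death covers 28 days (9.3.2.1.6). Infant data may be in the mother's claims for about 30 days (9.3.2.1). Since 28 < 30, the outcome window lies wholly inside that period.

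**2. Which file is searched, by outcome.**
- Malformations (9.3.2.1.1): infant's data to 1 year, mother's claims for the first 30 days.
- Small for gestational age (9.3.2.1.2), low birth weight (9.3.2.1.4) and NICU admission (9.3.2.1.5): both files, first 30 days.
- Preterm birth (9.3.2.1.3): taken from the pregnancy-duration algorithm, which works from codes around the delivery encounter.
- Neonatal death (9.3.2.1.6): discharge disposition, file not stated.

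Neonatal death is the only infant outcome with neither a two-file search nor a route through the delivery encounter.

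**3. Two separate routes of loss.**
- Route A: the infant is linked, but the fatal stay is filed under the mother. The pregnancy stays in the denominator and the death may be missed.
- Route B: the infant dies before having a record and is never linked. The pregnancy leaves both numerator and denominator.

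Extending the search addresses route A. Route B comes from the linked-only cohort and needs a different denominator.

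**4. What sizing would require.** Let L be the proportion of surviving infants linked, L_d the proportion of neonatal deaths linked, and c the proportion of linked deaths captured. With deaths rare,

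reported prevalence / true prevalence ≈ (L_d / L) × c.

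Section 9.2.1 gives overall linkage of about 74% and section 9.9.1 gives 70% to 80%. With deaths rare, either is close to L. Neither L_d nor c is given. As an illustration only, take L = 0.74, L_d = 0.37 (assumed) and c = 1: the ratio is 0.37 / 0.74 = 0.50. If the two routes together lost 25% to 75% of deaths relative to survivors (assumed), the reported figure would be 75% to 25% of the true one. If L_d = L and c = 1, nothing is lost. The documents do not narrow this range.

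**5. Effect on the comparison.** If the ratio in step 4 is the same in both exposure groups, it cancels from the risk ratio. What remains is a prevalence that is too low and fewer events. Nothing in the protocol suggests that the loss differs by exposure.

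**6. What is disclosed.** Section 9.9.1 gives one cause for missed neonatal deaths, reliance on discharge data. It discloses incomplete linkage separately, but the selection mechanism it explains is an association between exposure and pregnancy loss. It does not mention delayed enrolment or linkage that depends on survival.

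**The case against.** The strongest reply is that the omission suits the data element. Malformations, small for gestational age and low birth weight are found by diagnosis codes and NICU admission by procedure codes. All of these can appear on a claim filed under the mother. Discharge disposition is an encounter-level field (section 9.4: alive, expired or unknown), and on a mother's own stay it would presumably describe the mother. Adding the words mother's claims to 9.3.2.1.6 would not by itself recover deaths. This stands in part, and it is why the fix needs a check on whose disposition it is. It does not make the search futile: the NICU rule itself looks for newborn inpatient services in the mother's claims, and section 9.3.2.1.5 cites a positive predictive value of 92% for NICU codes recorded in the two files.

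Much is also disclosed. Section 9.9.1 calls neonatal death rare and subject to under-ascertainment, and defers bias assessment to the SAP, which is not at hand. Section 9.3.2 plans a literature search for validated algorithms for the secondary outcomes. These points lower the weight of the concern, but they do not settle which file 9.3.2.1.6 means.

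Power would be low anyway. At an assumed unexposed risk of 0.8% with full capture, 711 exposed and 2133 unexposed infants give about 47% power for a risk ratio of 2 (two-sided 5%). This stands for the comparison, but the stated objective is prevalence.

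Three stronger readings are tempting and not supported:
- A reader might infer that deaths before the infant has its own record are certainly not counted. The protocol says only that infant data may be in the mother's claims, 9.3.2.1.6 does not expressly exclude the mother's file, and 9.2.1 lets each Data Partner link with all local resources. That early deaths go unlinked is an inference.
- A reader might infer that the protocol has already solved this for the other four outcomes. For unlinked infants it has not, because the linked-only restriction applies to them all.
- A reader might apply a loss fraction to 711 and 2133 to count missing deaths. Section 9.5 defines those as infants already linked, so deaths lost before linkage cannot be subtracted from them.

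**Conclusion.** The concern holds as a gap in ascertainment. Neonatal death is absent from the two-file search although its window lies inside the period that motivates that search. Section 9.3.2.1.6 does not say whose files are used, and the linked-only cohort may drop the earliest deaths. Section 9.9.1 names neither delayed enrolment nor survival-dependent linkage as a cause.

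The direction is towards too low a prevalence. The size cannot be determined from the protocol: it depends on how often early deaths are linked and on how each Data Partner files newborn stays. The primary objective is unaffected. This is a cheap improvement to one secondary safety outcome, not a threat to the study.

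**What to change.** - In 9.3.2.1 and 9.3.2.1.6, add neonatal death to the outcomes searched in both infants' and mothers' claims, through day 28. Count a newborn inpatient stay filed under the mother's identifier with a disposition of expired only after checking that the disposition is the newborn's, for example by later activity in the mother's own claims.
- As a sensitivity analysis, report neonatal death over all eligible live-birth deliveries irrespective of linkage, beside the linked-only estimate. The Secondary Objective 2 population in 9.2.1 carries no linkage condition, so these deliveries are already identified. For unlinked deliveries only the mother's file can be searched, so this estimate may still be too low; the two should be read together.
- In 9.9.1, name delayed enrolment and survival-dependent linkage as causes of under-ascertainment of neonatal death.

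The cost is one more outcome in a 30-day mother's-claims query that is already planned, plus a check of a few flagged records. The yield is uncertain, because it depends on how each Data Partner files newborn stays.
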